Protocol Abstract Page

A Phase II Study of Ipilimumab PLUS Androgen Deprivation Therapy in Castrate Sensitive Prostate Carcinoma 2009-0378

Core Protocol Information

Study Chairman:	[name]
Department:	Genitourinary Medical Oncology
Full Title:	A Phase II Study of Ipilimumab PLUS Androgen Deprivation Therapy in Castrate Sensitive
	Prostate Carcinoma
Protocol Phase:	Phase II
Version Status:	Activated Closed to new patient entry as of 10/11/2013
Version:	15
Document Status:	Final

Abstract

Objectives:

Primary Objectives:

• To estimate the rate of PSA </= 0.2ng/mL at 7 months in patients treated with androgen deprivation therapy (ADT) plus Ipilimumab.

Secondary Objectives:

- To profile *immunological changes* induced in patients with metastatic prostate carcinoma treated with intermittent ADT plus Ipilimumab.
- To assess the *time to testosterone recovery* (> 50ng/mL) in patients treated with intermittent ADT plus Ipilimumab.
- To assess the *time to PD off ADT*, after treatment with intermittent ADT plus Ipilimumab.
- To characterize **safety** and drug-related adverse events of ipilimumab combined with complete androgen ablation.
- To determine the *overall survival* of patients treated with intermittent ADT and ipilimumab.

Rationale: (Be as concise as possible)

Androgen ablation induces involution of prostate cancer at both primary and metastatic sites. Androgen

ablation also leads to an accumulation of mononuclear cells within the prostate, (which is associated with a better prognosis of the disease) and the development of new seroreactivities in patients with prostate cancer. These findings suggest that the induction of specific T cell responses might contribute to the anti-tumor effect of androgen ablation. Enhancing the host immune response against the tumor might lead to an improvement in the outcome of patients with metastatic prostate carcinoma.

T cell activation is a complex process that is initiated when an antigen is presented to the T cell receptor (TCR) followed by the interaction of additional T cell surface molecules with their respective ligands on the antigen presenting cell (APC). This second interaction can result in a positive or a negative costimulatory signal depending on which specific molecules are involved. CTLA-4 is a T-cell surface molecule that, on interaction with the B7 molecule of the APC, leads to the termination of the T-cell response. Blockage of CTLA-4 with the monoclonal antibody Ipilimumab has led to a remarkable enhancement of the immune response in experimental models of cancer and infection.

Durable responses and SD after treatment with ipilimumab have been observed in several malignancies, including melanoma, prostate and renal cell carcinoma.

Eligibility: (List All Criteria)

Inclusion:

- 1) Histologically or cytologically confirmed prostate carcinoma.
- 2) Evidence of metastatic disease on previous bone scan and/or CT scan and/or MRI.
- 3) Castrate-sensitive disease. Patients already on ADT are eligible as long as the time from initiation of LHRH analog or antagonist is not greater than 1 month AND the total exposure time to the LHRH analog or antagonist will not exceed 8 months (i.e. the effectiveness of current depot LHRH analog or antagonist does not extend beyond 8 months since its initiation).
- 4) Patients who have received prior hormonal therapy are allowed to participate as long as they have been off hormone ablation for 1.5 times as long as they were on it: e.g. 1) Patients who have received up to 4 months of hormonal ablation are eligible as long as they have been off hormonal ablation for >/= 6 months; 2) Patients who have received 1 year of hormonal ablation are eligible as long as they have been off hormonal ablation for >/= 18 months; 3) Patients who have received up to 2 years of hormonal ablation are eligible as long as they have been off hormonal ablation for >/= 3 years have elapsed since its discontinuation.
- 5) ECOG performance status </= 1
- 6) Patients must have normal organ and marrow function as defined below: a) WBC >/= 3000/uL; b) ANC >/= 1500/uL; c) Platelets >/= 100×10^3 /uL; d) Hemoglobin >/= 9 g/dL; e) Creatinine </= 2 mg/dL; f) ALT </= 2.5×10^3 ULN for patients without liver metastases. For patients with liver metastasis ALT </= 5×10^3 ULN is allowed; g) Bilirubin </= 3×10^3 ULN (except for patients with Gilbert's Syndrome, who must have a total bilirubin </= 3×10^3 Mg/dL)
- 7) Patients included in the study must be >/= 18 years old
- 8) Ability to understand and willingness to sign a written informed consent document.

Exclusion:

1) Autoimmune disease: Patients with a history of inflammatory bowel disease (including Crohn's disease and ulcerative colitis) and autoimmune disorders such as rheumatoid arthritis, systemic progressive sclerosis [scleroderma], Systemic Lupus Erythematosus or autoimmune vasculitis [e.g.,

Wegener's Granulomatosis] are excluded from this study.

- 2) Any underlying medical or psychiatric condition, which in the opinion of the Investigator, will make the administration of study drug hazardous or obscure the interpretation of AEs: e.g. a condition associated with frequent diarrhea or chronic skin conditions, recent surgery or colonic biopsy from which the patient has not recovered, or partial endocrine organ deficiencies.
- 3) Patients with known brain metastases.
- 4) Patients with small cell carcinoma of the prostate.
- 5) History of other malignancies, other than nonmelanoma skin cancer or Ta or T1 (low grade) bladder carcinomas, unless in complete remission and off therapy for that disease for at least 5 years.
- 6) Uncontrolled intercurrent illness including, but not limited to, ongoing or active infection, history of congestive heart failure, unstable angina pectoris, cardiac arrhythmia, or psychiatric illness/social situations that would limit compliance with study requirements.
- 7) Known HIV, Hepatitis B, or Hepatitis C.
- 8) Untreated symptomatic spinal cord compressions.
- 9) Any non-oncology vaccine therapy used for prevention of infectious diseases (for up to one month prior to or after any dose of ipilimumab).
- 10) Concomitant therapy with any of the following: IL-2, interferon or other non-study immunotherapy regimens; cytotoxic chemotherapy; immunosuppressive agents; other investigation therapies; or chronic use of systemic corticosteroids (used in the management of cancer or non-cancer-related illnesses).
- 11) Previous participation in another ipilimumab clinical trial or prior treatment with a CD137 agonist or CTLA-4 inhibitor or agonist.
- 12) History of acute diverticulitis, intra-abdominal abscess, GI obstruction, abdominal carcinomatosis or other known risk factors for bowel perforation.
- 13) Patients who do not agree to practice appropriate birth control methods while on therapy.
- 14) Concurrent use of 5-alpha reductase inhibitors (finasteride or dutasteride).

Is there an age limit? Yes

Why? Provide scientific justification:

Prostate cancer does not occur in patients under the age of 18.

[figure not shown]
Disease Group:

Prostate

[figure not shown]
Treatment Agents/Devices/Interventions:

Degarelix, Goserelin Acetate, Ipilimumab, Leuprolide Acetate

Proposed Treatment/Study Plan:

Schema: Study Phases

	Pre-study Evaluation	On-Study h Evaluation	Prior to each Dose of Ipi and every 4 weeks for 6 months after last dose of ipi	Every 12 weeks beginning 6 months after last dose of Ipi	Disease Progression (+/- 14 days of the time the patient enters on study follow- up)	Long-ter up (every after o progressi months dose
Physical Exam (interim history pertaining to current medications and treatment related toxicities)	x ^b	x	х	х	х	
CT Abd/Pelvis (preferred) or k MRI Abd/Pelvis	x ^a				х	
Chest X-ray	x ^{a,d}				x ^d	
Bone Scan	Х ^а				X	
Complete Medical History	x ^b					
Electrocardiogram	х ^b					
Height	xc					
Weight	xc					
PS (ECOG)	xc					
BP, Pulse, Temperature	xc					
Concurrent Medications	xc	х	x	х	x	
Baseline Toxicity Evaluation	x ^c					
CBC with diff. and plt.	xc	X	X	x ^j	X	
Serum Chemistry	x ^c	х	х	х	x	
Urine N-telopeptides (NTX)	x ^c	X	х	x ^j		

PSA Assessment	x ^{c,f}	X	x	X	x	
Serum Testosterone Levels	x ^{c,g}	х	x	X	x	
Autoimmune Panel	Хc					
ACTH	Х ^с	X	X	X	X	
Cortisol	xc	Х	X	X	x	
TSH	Х ^с	X	X	X	X	
Free T4	xc	X	X	x	x	
Amylase	Хc	X	X	X	x	
Lipase	xc	X	x	x	x	
SPEP and anti-TPO titer	xc	X	x	x	x	
Adverse Events			X	X	X	
Correlative Studies		X	X	X	x	
Survival						X

Legend

- a = Within 42 days of study entry +/- 3 days
- b = Within 28 days of study entry +/- 3 days
- c = Within 14 days of study entry +/- 1 day
- d = If lung metastases are evident on chest x-ray, CT of the chest should be obtained as well
- e = Must include: creatinine, BUN, sodium, chloride, CO2, potassium, calcium, magnesium, phosphorus, glucose, albumin, total protein, total bilirubin, SGOT [AST], SGPT (ALT), alkaline phosphatase, bone alkaline phosphatase (ALP) and LDH
- f = for patients registered after initial androgen ablation, PSA must have been assessed within 3 weeks prior to androgen ablation initiation and that will be considered as baseline
- g = for patients registered after initiation of androgen ablation serum testosterone levels are preferable within 3 weeks prior to initiation of androgen ablation, though lack of this information will be acceptable for these patients
- h = On study tests/visits that must occur within a defined time frame shall have a standing window of allowance that is equal to +/-2 days for any laboratory testing
- i = Adverse events will be monitored using the NCI CTCAE Version 3.0
- j = Bone alkaline phosphatase and urine N-telopeptides (NTX) at Week 25 (month 7)
- k = Restaging scans or other disease assessment diagnostics during study are at the discretion of study collaborator or the principal investigator and shall be performed if disease progression is suspected
- I = 90mL of peripheral blood will be collected and may be banked for future research related to immunologic response

Table 2. Regimen Description.						
Agent	Dose	Route	Schedule	Duration		
LHRH Analogue (one of the following) or Antagonist						
Leuprolide	7.5mg*	IM	Once a month*	8 months		
Goserelin	3.6mg*	SC	Once a month*	8 months		
Degarelix	80mg	SC	Once a month	8 months		
2. Ipilimumab						
	10mg/kg	IV over	Once every 4			
		90 min**	weeks x 4			

^{*} Leuprolide 22.5mg or Goserelin 10.8mg every 3 months can be used for ADT as long as the total duration of ADT does not exceed 8 months. For example, a 3-month depot formulation can be used for the first six months, followed by two 1-month depot formulations, to complete 8 months of ADT.

Statistical Considerations:

This is a single arm phase II trial to evaluate the rate of PSA \leq 0.2ng/mL in patients treated with ADT plus Ipilimumab. The primary endpoint is the proportion of patients achieving a PSA \leq 0.2ng/mL at month 7.

The trial was originally designed to use a Simon's optimal two-stage design to stop the trial if 7 or less among the first 16 patients achieved a PSA \leq 0.2ng/mL at month 7. However, since then ipilimumab has been approved by the FDA for use in melanoma patients and there are data showing that the full effect of immunotherapies can take many months (possibly longer than 7) to become evident. On the other hand, the accrual rate for this trial has been faster than we originally expected. Since its activation on 06/17/2011, we have already enrolled 9 patients. Given the fast accrual rate and the desirability of a longer wait time and of data from the secondary endpoints to reliably assess efficacy, we now propose to change the study to a single-stage design for efficacy endpoint. Based on new safety data obtained since the trial was first designed, the safety monitoring plan has also been changed as described below. We will perform a final analysis on the primary and secondary efficacy endpoints when the study is complete.

Let S be the event of achieving PSA \leq 0.2ng/mL at month 7. It is assumed that ADT plus Ipilimumab will have a target rate of 60% for S. A rate of 40% or lower is considered a failure and the combination therapy will be rejected under this circumstance. With a sample size of 48 patients, we will have an 80% power to detect such a 20% difference using a Chi-squared test and with a two-sided type I error rate of 0.05. The sample size was computed using nQuery Advisor 7.0.

Safety Monitoring and Rules:

The PI will meet with the research nurse and data coordinator regularly to monitor toxicity events. Toxicity reports will be generated monthly and reviewed by the PI and the statistician. If at any time during the study, one of the following criteria is met, then accrual will be suspended until the PI has reviewed the events and determined the appropriate course of action, which could include a protocol amendment to decrease the dose of ipilimumab.

- ≥ 40% of subjects treated on the ipilimumab arm develop a ≥ Grade 3 toxicity thought to be related to the ipilimumab.
- > 10% of subjects experience an ipilimumab related > Grade 3 toxicity that cannot be alleviated or controlled by appropriate care and/or steroid and/or infliximab therapy within 14 days of the initiation of such therapy

^{**} Ipilimumab administration will be allowed a standing window for completion of the infusion +/- 10 minutes of targeted time.

Any 2 ipilimumab related deaths unless also attributed to progression have occurred

Endpoint Definitions and Analysis Plan

For the primary analysis, the proportion of patients achieving PSA < 0.2ng/mL at 7 months will be estimated in the ITT population, along with the exact 95% confidence interval. Kaplan-Meier methods will be used to analyze the time-to-event outcomes, including:

- 1. Time to testosterone recovery: Defined as the time between day 224 of the protocol and the date at which serum testosterone returns to > 50ng/mL. As per Section 5.1, the effect of ADT should not last beyond 8 months, i.e. beyond day 224. Patients who have not achieved testosterone recovery (ie, returns to > 50ng/mL) at the last follow-up time will be treated as censoring.
- 2. Time to PD off ADT: defined as the time between day 224 of the protocol and the date of the first PSA measurement that is ≥20% above the nadir, as long as the rise is confirmed by a two additional PSA measurements separated by at least one week as described in Section 7.2. Patients who have not experienced PSA progression at the last follow-up time will be treated as censoring.
- 3. Overall survival: defined as the time between the date of registration and the date of death. Patients who have not died at the last follow-up time will be treated as censoring.

Note: For patients who experience SAEs prior to 7 months, treatment will be discontinued. However, these patients will continue to be followed-up for the efficacy assessment. They will be counted as successes for PSA response if they achieve a PSA level less than or equal to 0.2ng/ml at 7 months.

Where Will Participants Be Enrolled:

Only at MDACC

Is this an NCI-Cancer Therapy Evaluation Protocol (CTEP)?

Is this an NCI-Division of Cancer Prevention Protocol (DCP)?

Estimated Accrual:

Total Accrual at MDACC: 48
Estimated monthly accrual at MDACC: 1-2

Accrual Comments:

Do you expect your target population to include non-english No speaking participants?

Location of Treatment:

This protocol is performed on an Outpatient basis.

Length of Stay: What is the length & frequency of hospitalization?

n/a

Return Visits: How often must participants come to MDACC?

Patients will return every 4 weeks for follow-up and treatment with ipilimumab for the first 32 weeks on study. Patients will return every 4 weeks for 6 months after last dose of Ipilimumab and every 12 weeks thereafter.

Home Care: Specify what, if any, treatment may be given at home.

n/a

Name of Person at MDACC Responsible for Data Management: [name]

Prior protocol at M. D. Anderson:

Has the Principal Investigator ever had a clinical or behavioral protocol at MDACC that accrued patients? Yes

Data Monitoring Committee:

Is treatment assignment randomized? No

Is this a blinded or double-blinded study? No

Does this protocol have a schedule for interim and final analysis? No

Radiation Safety:

Does this study involve the administration of radioisotopes or a radioisotope labeled agent?	No	
Is the radioactive compound (or drug) FDA approved and/or commercially available?	No	

Investigational New Drugs:

Does this protocol require an IND? Yes

Please list the IND holder and provide the IND number:

IND Holder: MDACC IND Number: 106,207

Investigational Device:

Is the	Investigational	Device	approved by the FDA?	N/A

Is the Investigational Device being used in the manner approved by N/A the FDA?

Has the Investigational Device been modified in a manner not N/A approved by the FDA?

Name of Device:

Manufacturer:

No

What is the FDA Status of the Investigational Device?

Is the study being conducted under an Investigational Device Exemption (IDE)?

IDE Holder:

IDE Number:

Risk Assessment:

Please answer the following questions regarding the Investigational Device.

Intended as an implant?

Purported or represented to be for use supporting or sustaining human life? No

For use of substantial importance in diagnosing, curing, mitigating, or treating No disease, or otherwise preventing impairment of human health?

You may attach sponsor documentation of the risk assessment:

Will participant be charged for the Investigational Device? No

Sponsorship and Support Information:

Does the Study have a Sponsor or Supporter? Yes

Sponsor or Supporter: Bristol-Myers Squibb

Type(s) of Support: Funds

Agent

Monitored by Sponsor or Sponsor Representaive (CRO)?

Is this Protocol listed on any Federal Grant or Foundation Funding Application? No

Biosafety:

Does this study involve the use of Recombinant DNA Technology?

Does this study involve the use of organisms that are infectious to humans? No

Does this study involve stem cells?

Technology Commercialization:

Does this study include any agents or devices manufactured or produced at No MD Anderson Cancer Center?

Laboratory Tests:

Where will laboratory tests be performed on patient materials? (Please select all that apply) Division of Pathology & Laboratory Medicine CLIA Certified Laboratory

Manufacturing:

Will you manufacture in full or in part (split manufacturing) a drug or biological product at the M. D. Anderson Cancer Center for the proposed clinical study?

No

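### Power and type I error are stated for a chi-squared test, the primary analysis is an exact 95% CI, and nothing says which decides efficacy; the two disagree at 26 of 48

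*Combined protocol and SAP*

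**What the plan says.** The Statistical Considerations describe a single-arm, single-stage trial with month-7 PSA response as the primary endpoint. The design values are:

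- target rate: "It is assumed that ADT plus Ipilimumab will have a target rate of 60% for S"
- failure rate: "A rate of 40% or lower is considered a failure and the combination therapy will be rejected under this circumstance"
- size and power: "With a sample size of 48 patients, we will have an 80% power to detect such a 20% difference using a Chi-squared test"
- error: "with a two-sided type I error rate of 0.05"

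The Endpoint Definitions and Analysis Plan then says that the month-7 response proportion "will be estimated in the ITT population, along with the exact 95% confidence interval". It names no test and no critical count, and does not compare the interval with 40%.

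The Primary Objectives are worded as estimation: "To estimate the rate of PSA </= 0.2ng/mL at 7 months in patients treated with androgen deprivation therapy". On timing the plan says "We will perform a final analysis on the primary and secondary efficacy endpoints when the study is complete", without naming a deciding method.

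**The concern.** The stated power and type I error belong to one method, and the primary analysis is another. That is harmless when the plan says which one carries the conclusion. Here it does not, although a failure rate, a target rate, an error rate and a statement that the combination will be rejected all imply a yes-or-no conclusion.

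Two things are at stake. First, if the two methods have different critical counts, some result could be called positive or negative depending on a choice made after the data are seen. Second, the stated 80% and 0.05 may not describe the analysis that is actually used.

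**Working it through.** **Inputs.** From the Statistical Considerations: p0 = 0.40, p1 = 0.60, n = 48, two-sided alpha 0.05, power 80%, one arm. From the Endpoint Definitions and Analysis Plan: exact 95% CI, taken here as Clopper-Pearson.

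**1. The plan's own figure.** For a one-sample chi-squared test without continuity correction,

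n = [z(0.975)·√(p0(1−p0)) + z(0.80)·√(p1(1−p1))]² / (p1−p0)²
= (1.96·√0.24 + 0.8416·√0.24)² / 0.2² = 47.09, rounded up to 48.

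Approximate power at n = 48 is Φ(0.2·√48/√0.24 − 1.96) = Φ(0.868) = 80.7%. The stated figure reproduces. Other forms do not give 48: one-sided 0.05 gives 38, the continuity-corrected form about 52, and a two-sample comparison 97 per arm.

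**2. Critical counts at n = 48.** The expected count under 40% is 48 × 0.4 = 19.2 and the variance is 48 × 0.24 = 11.52.

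| Responders | Uncorrected chi-squared p | Corrected chi-squared p | Exact binomial p | Exact 95% CI |
|---|---|---|---|---|
| 25 (52.1%) | 0.087 | 0.118 | 0.105 | 37.2% to 66.7% |
| 26 (54.2%) | 0.045 | 0.063 | 0.055 | 39.2% to 68.6% |
| 27 (56.3%) | 0.022 | 0.032 | 0.026 | 41.2% to 70.5% |

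At 26, chi-squared = (26 − 19.2)²/11.52 = 4.01. The uncorrected test therefore succeeds from 26 and the exact CI from 27. On the downward side both reject 40% at 12 or fewer, so 26 is the only count where they disagree.

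**3. Exact binomial properties, n = 48.**

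| Rule | Upper-tail error at 40% | Lower tail (12 or fewer) | Two-sided error | Power at 60% |
|---|---|---|---|---|
| Exact CI, 27 or more | 1.66% | 2.19% | 3.85% | 75.3% |
| Uncorrected chi-squared, 26 or more | 3.28% | 2.19% | 5.48% | 83.5% |

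Under the exact-CI rule, 80% power is reached at a true rate of about 61.1%.

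**4. How likely is the disputed count?** The probability of exactly 26/48 is 1.6% at a true 40%, 11.4% at 55% and 8.2% at 60%.

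**5. Sensitivity to the final ITT number.** The exact-CI cut-off and its power at 60% are:

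| ITT n | Cut-off | Power at 60% |
|---|---|---|
| 46 | 26 | 73.8% |
| 47 | 26 | 79.0% |
| 48 | 27 | 75.3% |
| 49 | 27 | 80.2% |
| 50 | 28 | 76.6% |

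Power is not monotone in n because the count is discrete, so the cut-off must be recomputed if the ITT number is not 48.

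**The case against.** The strongest reply is that nothing conflicts. The chi-squared test is the only test named, so it decides, and the exact CI only reports precision, in keeping with an estimation objective. Sizing on a test and reporting an exact interval is common. On that reading exact power is 83.5%, so 80% is slightly conservative, and the two-sided 5.5% includes a lower tail that could never support an efficacy claim; the relevant error is 3.3% against a nominal 2.5%. Only the uncorrected form gives 48 patients, so the plan's figures largely settle the continuity question. One count is affected, and the count and interval will be published anyway. Finally, the analysis plan cites Sections 5.1 and 7.2, which are not in the text supplied, so a rule might exist elsewhere.

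Much of this stands. The sample size is correct, the shortfall in power depends on the exact CI or a corrected test deciding, and the practical reach is one count. But the reading that the chi-squared test decides is an inference. The test appears only in the sample-size justification, and the one inferential method listed for the primary analysis is the exact CI. Under either reading a stated figure is missed: the exact-CI rule falls below 80% power, and the chi-squared rule exceeds a two-sided 0.05. If a deciding rule exists elsewhere, citing it and aligning these two sections would close the point.

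**Conclusion.** The concern holds and should be fixed; it is not a fatal flaw. The sample size is not an arithmetic error. The defect is that the stated operating characteristics belong to a method that the primary analysis does not name, and no deciding rule is given. If the exact CI decides, true power at 60% is about 5 points below the stated 80%. If the uncorrected chi-squared test decides, two-sided error is about half a point above the stated 0.05. A result of 26/48 could be called either way.

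This rests on three assumptions: the exact interval is Clopper-Pearson, the final ITT number is 48, and the chi-squared test is uncorrected, as the sample size implies. With a continuity correction the test would agree with the exact CI at 26/48, and the shortfall in power would apply to it as well. The absence of a rule is established for the supplied text only.

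**What to change.** Name the exact 95% CI as the deciding method, since the analysis plan already specifies it and its two-sided error stays below 0.05. Efficacy would be claimed if the lower limit exceeds 40%, which means at least 27 of 48. State that the cut-off is recomputed if the ITT number is not 48. Restate power as about 75% at a true 60% (80% at about 61%) and upper-tail error as 1.7%.

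If the sponsor prefers to keep the chi-squared test, say that it is uncorrected, give the rule as at least 26 of 48 with about 83% exact power and 5.5% two-sided error, and say that the CI is for reporting only.

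In either case, date the choice and state whether month-7 PSA results were already known when it was made; accrual is closed, so a reader will ask.

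The cost is two or three sentences in the statistical section, with no added patients or data. If the exact CI decides, the sponsor also accepts a less favourable power figure.

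### Testosterone recovery is defined as a level above 50 ng/mL (5,000 ng/dL), so the endpoint as written would have essentially no events

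*Combined protocol and SAP*

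**What the plan says.** The recovery threshold appears three times in the combined protocol and SAP, each time with the same unit:

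- **Abstract, Secondary Objectives.** The objective on time to testosterone recovery gives the level as "> 50ng/mL) in patients treated with intermittent ADT plus Ipilimumab".
- **Endpoint Definitions and Analysis Plan, item 1, event.** Time runs from day 224 to "the date at which serum testosterone returns to > 50ng/mL".
- **Endpoint Definitions and Analysis Plan, item 1, censoring.** "Patients who have not achieved testosterone recovery (ie, returns to > 50ng/mL) at the last follow-up time will be treated as censoring".

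The same section names the method: "Kaplan-Meier methods will be used to analyze the time-to-event outcomes". Statistical Considerations sets the timing: "We will perform a final analysis on the primary and secondary efficacy endpoints when the study is complete".

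The study schema has a row for "Serum Testosterone Levels", with measurements before study, on study, through follow-up and at progression. For men who started ADT before registration, note g of the legend prefers a pre-ADT value, "though lack of this information will be acceptable for these patients".

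The text available for review gives no testosterone reference range, castrate level, expected recovery rate or assay unit. Item 1 refers to Section 5.1, which is not in that text.

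**The concern.** The endpoint is meant to measure how long testosterone takes to come back once the effect of ADT has ended. A usable threshold must be one that a recovered man passes. A level of 50 ng/mL appears to lie far above anything he would reach, so a man fully back in the normal range would still be classed as not recovered.

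Applied literally, the rule would censor essentially every patient. The curve for remaining unrecovered would stay at 1.0 and no median could be estimated. A reader could take that for lasting testosterone suppression in the whole cohort, when it would only reflect the threshold. The plan gives the wish for secondary-endpoint data as one reason for moving to a single-stage design, so this endpoint is more than decoration.

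**Working it through.** **The plan's own figure.** The plan states no event count or rate for testosterone recovery. The only design figure to reproduce is the sample size for the primary endpoint: "With a sample size of 48 patients, we will have an 80% power to detect such a 20% difference". With rates of 40% and 60% and two-sided alpha of 0.05, the one-sample formula gives

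n = (1.960 × √(0.4 × 0.6) + 0.842 × √(0.6 × 0.4))² / 0.2² = 47.09, rounded up to 48, with power 80.7% at 48.

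The figure reproduces. It is used below only as the number of patients.

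**Unit conversion.** 50 ng/mL × 100 mL/dL = 5,000 ng/dL. Conversely, 50 ng/dL ÷ 100 = 0.5 ng/mL.

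**Assumption.** Because the documents give no reference range, one is assumed for adult men: an upper limit U of 8 to 20 ng/mL and a lower limit L of 3 ng/mL, repeated with L = 2. Values in recovered men are taken as log-normal, with L and U as the 2.5th and 97.5th percentiles:

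- mean of log values: m = (ln L + ln U) / 2
- SD of log values: s = (ln U − ln L) / 3.92
- P(value > 50) = 1 − Φ((ln 50 − m) / s)
- expected events = 48 × P, taking one value per patient and all 48 as recovered

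Worked case, L = 3 and U = 20: m = 2.047, s = 0.484, z = (3.912 − 2.047) / 0.484 = 3.85, P = 5.8 × 10⁻⁵, and 48 × P = 0.0028. The chance of even one event is 0.28%.

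| U (ng/mL) | 50 / U | P, L = 3 | Events of 48, L = 3 | P, L = 2 | Events of 48, L = 2 |
|---|---|---|---|---|---|
| 8 | 6.25 | 8 × 10⁻²¹ | below 10⁻¹⁰ | 4.6 × 10⁻¹³ | below 10⁻¹⁰ |
| 10 | 5.0 | 3.0 × 10⁻¹³ | below 10⁻¹⁰ | 2.1 × 10⁻⁹ | 9.8 × 10⁻⁸ |
| 15 | 3.33 | 5.0 × 10⁻⁷ | 0.00002 | 8.5 × 10⁻⁶ | 0.0004 |
| 20 | 2.5 | 5.8 × 10⁻⁵ | 0.0028 | 2.2 × 10⁻⁴ | 0.010 |

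**Repeated measurement.** With 20 values per patient (48 × 20 = 960 values), L = 3 and U = 20, the expected number of values above 50 ng/mL is 960 × 5.8 × 10⁻⁵ = 0.056.

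**Stretching the range.** With L = 3 and U = 30 ng/mL, the expected number of events is 0.11 of 48. If the upper limit were 50 ng/mL itself, 2.5% of men would exceed it on a single value: 48 × 0.025 = 1.2 events.

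**The other unit.** In the same model P(value > 0.5 ng/mL) exceeds 0.99999 at every combination in the table, so 48 × P rounds to 48.0 of 48.

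**The case against.** The documents do not contradict themselves here. The unit is the same wherever it appears, and no range, castrate level or assay unit is given against which it fails. The case rests on an assumed reference range. That is true, and it is why the range is stated openly and varied. The conclusion holds across it, and the normal range would have to extend well above 50 ng/mL before the definition worked.

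The probabilities are also more precise than the assumption deserves. They extrapolate a log-normal curve far beyond its fitted limits, and the small counts move with the lower limit: the largest rises from 0.003 to 0.010 when it drops from 3 to 2 ng/mL. The result of 48.0 of 48 under ng/dL is close to true by construction, since it presumes all 48 have recovered. This is fair. The conversion and the ratio carry the point, and the probabilities only show scale.

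Two of the three statements sit in the same item, so they are not three independent confirmations. They still need three edits. The full protocol, including Section 5.1, might give another unit. That cannot be checked here, and it is a reason to ask the sponsor rather than to assert ng/dL.

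Finally, an analyst might spot the slip and use ng/dL without comment, and the trial is already closed to new patients. But a silent correction departs from the written definition, and a derivation programmed from the text would apply it literally. The final analysis is where the definition matters, and closure to entry does not alter that.

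**Conclusion.** The concern holds: the threshold is wrong as written and should be fixed. At 5,000 ng/dL it is 2.5 to 6.25 times an assumed upper limit of 20 down to 8 ng/mL. At most about 0.01 events would be expected among 48 fully recovered men, so time to testosterone recovery could not be estimated. Read as 50 ng/dL, the result reverses.

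Confidence is high in the literal reading and the conversion. That the endpoint would be empty depends on the assumed range but is insensitive to it. That ng/dL was intended is an inference the documents cannot prove.

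The damage is confined to this one secondary endpoint. Because testosterone values are scheduled for collection, the event can be re-derived and no data are lost. The primary PSA endpoint, the sample size of 48 and the safety suspension rules do not depend on it. Since a pre-ADT testosterone value may be absent, nothing is claimed here about individual patients' earlier levels.

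**What to change.** The sponsor should confirm the intended threshold and its unit, checking against the unit in which the laboratory reports testosterone. It should then correct the secondary objective, the event definition and the censoring rule together, along with any matching text in the full protocol, including Section 5.1 if it repeats the figure. The laboratory's reporting unit should be stated beside the threshold. This must be done before the endpoint is derived for the final analysis.

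The cost is one confirmation and three unit edits in the text reviewed here. No new data are needed, and the primary endpoint and sample size do not change.
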